### 7.3. Vital Signs

Descriptive statistics will be provided by treatment group for body weight and vital signs as follows:

- Baseline value
- Values at each postbaseline visit
- Change from baseline at each postbaseline visit

A baseline value will be defined as the last available value collected on or prior to the date/time of first dose of study drug. Change from baseline to a postbaseline visit will be defined as the postbaseline value minus the baseline value. Vital signs measured at unscheduled visits will be included for the baseline value selection.

Median (Q1, Q3) of the observed values for vital signs will be plotted by treatment group and visit.

In the case of multiple values at a visit assessment, data will be selected for analysis as described in Section 3.8.3. No formal statistics testing is planned.

A by-subject listing of vital signs will be provided by subject ID number and visit in chronological order. Body weight, height and BMI will be included in the vital signs listing, if space permits. If not, they will be provided in the baseline characteristics listing given they were only collected at the Screening/Baseline visit.

## **7.4. Prior and Concomitant Medications**

Medications collected at screening and during the study will be coded using the current version of the World Health Organization (WHO) Drug dictionary.

### **7.4.1. Prior Medications**

Prior medications are defined as any medications taken before a subject took the first study drug.

Prior medications will be summarized by Anatomical Therapeutic Chemical (ATC) drug class Level 2 and preferred name using the number and percentage of subjects for each treatment group and overall. A subject reporting the same medication more than once will be counted only once when calculating the number and percentage of subjects who received that medication. The summary will be ordered alphabetically by ATC medical classes and then by preferred term in order of descending overall frequency with in each ATC medical class. For drugs with the same frequency, sorting will be done alphabetically.

For the purposes of analysis, any medication with a start date prior to the first dosing date of study drug will be included in the prior medication summary regardless of when the stop date is. If a partial start date is entered the medication will be considered prior unless the month and year (if day is missing) or year (if day and month are missing) of the start date are after the first dosing date. Medications with a completely missing start date will be included in the prior medication summary, unless otherwise specified. Summaries will be based on the Safety Analysis Set. No formal statistical testing is planned.

Prior ribavirin, palivizumab, and IVIG use will be summarized separately from other prior general medications.

### **7.4.2. Concomitant Medications**

Concomitant medications are defined as medications taken while a subject took study drug. Use of concomitant medications will be summarized by Anatomical Therapeutic Chemical (ATC) drug class Level 2 and preferred name using the number and percentage of subjects for each treatment group. A subject reporting the same medication more than once will be counted only once when calculating the number and percentage of subjects who received that medication. The summary will be ordered alphabetically by ATC medical class and then by preferred term in descending overall frequency within each ATC medical class. For drugs with the same frequency, sorting will be done alphabetically.

For the purposes of analysis, any medications with a start date prior to or on the first dosing date of study drug and continued to be taken after the first dosing date, or started after the first dosing date but prior to or on the last dosing date of study drug will be considered concomitant medications. Medications started and stopped on the same day as the first dosing date or the last dosing date of study drug will also be considered concomitant. Medications with a stop date prior to the date of first dosing date of study drug or a start date after the last dosing date of study drug will be excluded from the concomitant medication summary. If a partial stop date is entered, any

medication with the month and year (if day is missing) or year (if day and month are missing) prior to the date of first study drug administration will be excluded from the concomitant medication summary. If a partial start date is entered, any medication with the month and year (if day is missing) or year (if day and month are missing) after the study drug stop date will be excluded from the concomitant medication summary. Medications with completely missing start and stop dates will be included in the concomitant medication summary, unless otherwise specified. Summaries will be based on the Safety Analysis Set. No formal statistical testing is planned.

Concomitant ribavirin, palivizumab, and IVIG use will be summarized separately from other concomitant general medications.

All prior and concomitant medications (other than per-protocol study drugs) will be provided in a by-subject listing sorted by subject ID number and administration date in chronological order.

### **7.5. Electrocardiogram Assessment**

Number and percent of subjects with new ECG abnormalities at postbaseline visits including those assessments obtained for the purpose of standard of care will be summarized by treatments. Only subjects with baseline ECG assessments will be included in this analysis.

A shift table of the central ECG assessments at postbaseline visit including those assessments obtained for the purpose of standard of care compared with baseline values will be presented by treatment group using the following categories: normal, abnormal, no new abnormality, new abnormality, or missing. The number and percentage of subjects in each cross-classification group of the shift table will be presented. Subjects with a missing value at baseline or postbaseline will not be included in the denominator for percentage calculation. No formal statistical testing is planned.

A by-subject listing for ECG central assessments and ECG abnormalities, including those not required by the protocol (ie, standard of care), will be provided by subject ID number and visit in chronological order.

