1.2.3. Nonclinical Pharmacology and Toxicology

The IC₅₀ for the inhibitory effect of presatovir on hERG potassium current was 7.8 μ M. Cardiovascular effects of presatovir were evaluated in dogs at doses up to 75 mg/kg. The principal hemodynamic findings were lower heart rate values, and higher arterial pulse and systolic pressure values. All hemodynamic effects dissipated by 22 hours post-dose. All electrocardiograms (ECGs) were qualitatively within normal limits, and no presatovir-related arrhythmias or abnormal waveforms were detected. Slight presatovir-related higher PR and QTc interval values were expected physiological responses secondary to concomitant presatovir-related lower heart rate values. These changes were not considered physiologically important in the context of this study.

In a repeat dose study, presatovir was administered by oral gavage for 4 weeks to young adult rats once daily at doses up to 100 mg/kg/day. Two animals administered 100 mg/kg/day were found dead during the dosing phase. Although the cause of death for these 2 animals was undetermined, an association with presatovir cannot be excluded. Based on the results of this study, the NOAEL for presatovir is 70 mg/kg/day, which corresponded to mean AUC_{0-t} and C_{max} values on Day 23 of the dosing phase of 96, 316 ng.h/mL, and 6028 ng/mL, respectively. In a repeat-dose study conducted in young adult dogs, presatovir was administered by oral gavage for 4 weeks at doses up to 20 mg/kg/day. The NOAEL for this study is 20 mg/kg/day, which corresponded to mean AUC_{0-t} and C_{max} values on Day 27 of the dosing phase of 129,831 ng.h/mL and 8081 ng/mL, respectively.

Presatovir was negative in the rat micronucleus study and did not cause mutations in the Ames assay or induce chromosomal damage in vitro with or without S9 metabolic activation. Thus, the potential for genetic toxicity is considered low.

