8.7.3. Other Safety Evaluations

Vital signs and ECG data will be summarized by the observed data and by the change from baseline at each time point. In comparison to pre-treatment (either screening or pre-dose on study Day 1) values, vital signs, and ECG measurements will additionally be summarized using pre-determined clinically relevant thresholds.

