### **7.6. Other Safety Measures**

A shift table of troponin results at postbaseline visit (including those obtained for the purposes of standard medical care) compared with baseline values will be presented by treatment group using the following categories: normal, abnormal, or missing. The number and percentage of subjects in each cross-classification group of the shift table will be presented. Subjects with a missing value at baseline or postbaseline will not be included in the denominator for percentage calculation. No formal statistical testing is planned.

If multiple troponin results exist for one visit due to multiple troponin assay tests performed, the results obtained from Troponin I test will be used for the analysis.

A by-subject listing for all troponin results, including those not required by the protocol (ie, standard of care), will be provided by subject ID number and visit in chronological order.

A data listing will be provided for subjects experiencing pregnancy during the study.

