#### **7.7. Changes From Protocol-Specified Safety Analyses**

In accordance with the DMC Charter, the initial safety DMC meeting was scheduled to occur after approximately 50% of the subjects were enrolled. The winter 2016/2017 RSV season resulted in a higher rate of enrollment for this study compared to previous RSV seasons. Due to quicker than expected enrollment and the time required to prepare for a DMC meeting, it would not have been possible to hold the planned DMC meeting prior to all subjects completing treatment with presatovir. Since the findings of the DMC would not have been actionable upon subjects in the study, the DMC Chairperson agreed to forgo the meeting

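### The SAP omits the ECG change-from-baseline and the ECG and vital-sign threshold summaries promised in the protocol and does not list this as a change, so some PR or QTc lengthening may reach no planned ECG summary

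*SAP*

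**What the plan says.** Protocol 8.7.3 makes two commitments. First: "Vital signs and ECG data will be summarized by the observed data and by the change from baseline at each time point". Second, with pre-treatment values as the comparison: "vital signs, and ECG measurements will additionally be summarized using pre-determined clinically relevant thresholds".

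SAP 7.5 plans three ECG outputs:
- "Number and percent of subjects with new ECG abnormalities at postbaseline visits", among subjects with a baseline ECG;
- a shift table of the central assessments against baseline, "using the following categories: normal, abnormal, no new abnormality, new abnormality, or missing";
- a by-subject listing of assessments and abnormalities.

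The output list in SAP section 13 matches this: Tables 15.11.9.1 and 15.11.9.2, Listing 16.2.8.3, and no ECG figure.

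For vital signs, SAP 7.3 keeps observed values and change from baseline but sets no thresholds.

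SAP 7.7 is reserved for changes from the protocol's safety analyses. It reports one item, the cancelled DMC meeting, ending: "Since the findings of the DMC would not have been actionable upon subjects in the study, the DMC Chairperson agreed to forgo the meeting".

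For troponin, SAP 7.6 says that when several assays exist at one visit, "the results obtained from Troponin I test will be used for the analysis".

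**The concern.** A change from baseline needs numeric measurements, and a threshold summary needs stated cut-offs. The SAP supplies neither for ECG, and no cut-offs for vital signs. Because SAP 7.7 is the place where such changes are declared, a reader who finds only the DMC item there would conclude that nothing else had changed.

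The protocol itself gives a reason to look at intervals. In the dog cardiovascular study (protocol 1.2.3), "Slight presatovir-related higher PR and QTc interval values were expected physiological responses" to a lower heart rate. A shift in PR or QTc is continuous, and a categorical reading picks it up only when the reader calls a new abnormality. The thorough QT study (protocol 1.2.4.3) gave single doses to healthy adults aged 18 to 45, whereas this trial gives 14 days of dosing to lung transplant recipients. The one scheduled DMC safety review was cancelled, so the end-of-study tables are the main place where a by-arm interval effect could be seen.

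**Working it through.** There is no stated figure to reproduce. The check sets the two documents side by side and then asks what the planned outputs could miss.

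**Step 1. Commitment against delivery**

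| Protocol 8.7.3 | SAP text | SAP outputs |
|---|---|---|
| ECG observed values | None in 7.5 | None |
| ECG change from baseline | None in 7.5; categorical shift only | 15.11.9.1 (shift), 15.11.9.2 (new abnormalities) |
| ECG thresholds | None in 7.5 | None |
| Vital signs observed and change | Present in 7.3 | 15.11.7.1.1 to 15.11.7.1.6, plus median plots |
| Vital-sign thresholds | None in 7.3 | None |

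Four of the five commitments have no matching output, and SAP 7.7 declares none of the four.

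**Step 2. What the categorical ECG outputs can and cannot show**

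Inputs are the adult cut-offs in protocol Appendix 5:
- QTc by value: 0.45 to 0.47 s is Grade 1, 0.48 to 0.49 s Grade 2, 0.50 s or more Grade 3.
- QTc by increase: under 0.03 s is Grade 1, 0.03 to 0.05 s Grade 2, 0.06 s or more Grade 3.
- PR: 0.21 to 0.25 s is Grade 1, above 0.25 s Grade 2.

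The starting and ending values below are assumed for illustration.

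- QTc 0.40 to 0.44 s. Change = 0.44 − 0.40 = 0.04 s. This is Grade 2 by the increase criterion, yet both values lie below 0.45 s, so both ECGs could be read as normal.
- QTc 0.46 to 0.51 s. By value this moves from Grade 1 to Grade 3. It is the same kind of abnormality as at baseline, so it could be read as no new abnormality.
- PR 0.165 to 0.198 s. Change = 0.033 s. Both values lie below 0.21 s, so the PR cut-offs miss it too. Only a change-from-baseline summary would show it.
- Abnormal baseline ECG, then a different finding. This is a new abnormality, and both the shift table and Table 15.11.9.2 count it.

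SAP 7.5 does not define a new abnormality, so how the central reader would classify the first two cases is unknown.

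**Step 3. How much signal the ECG schedule could yield**

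Protocol 6.7.7 schedules a pre-dose Day 1 ECG and a Day 28 ECG. One further ECG is required only if the subject is at the site between Days 2 and 14. The last planned dose is on Day 14, so Day 28 comes 28 − 14 = 14 days later. With the multiple-dose half-life of about 36 hours (protocol 1.2.4.1), that is 14 × 24 / 36 = 9.3 half-lives. Day 28 therefore says little about an on-treatment effect. Summaries that pool it with Days 2 to 14 would dilute one.

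**Step 4. Troponin (minor)**

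Take a visit with a normal Troponin I and an abnormal Troponin T. Under SAP 7.6 it is analysed as normal.
- If that visit is post-baseline and baseline was normal, an apparent shift is removed.
- If that visit is baseline and a later result is abnormal, an abnormal-to-abnormal pair becomes normal-to-abnormal, and an apparent shift is added.

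The rule also allows the baseline and post-baseline results to come from different assays.

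**The case against.** The strongest reply is that little is lost in practice. Four parts of it stand.

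- **The shift is not a plain normal/abnormal table.** A reader might infer that a subject with an abnormal baseline ECG stays abnormal whatever happens next. The SAP does not support that: it has categories for new and no new abnormality, and a separate table of new abnormalities.
- **Heart rate and systolic pressure are not hidden.** A reader might infer that all the nonclinical cardiovascular signals are reduced to categories. In fact Tables 15.11.7.1.2 and 15.11.7.1.3 summarise systolic pressure and pulse as continuous changes from baseline. Only the ECG intervals lack this.
- **Prior evidence is reassuring.** The protocol judged the dog changes not physiologically important. The thorough QT study was negative at 200 and 800 mg. By simple superposition with a 36-hour half-life, accumulation is 1 / (1 − 2^(−24/36)) = 1 / (1 − 0.63) = 2.7. Thus 100 mg daily corresponds roughly to a 270 mg single dose, well under 800 mg. The first-in-human study found no clinically significant interval increase, though its highest multiple dose was 75 mg daily for 7 days.
- **Other routes exist.** SAP Appendix 3 includes the QT prolongation SMQ and selected ECG investigation terms among the cardiac adverse events of interest. All troponin results are listed by subject.

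It might also be said that the missing tables are what prevent the trial from reporting interval effects. That is too strong, because the visit schedule in Step 3 is the larger limit. Nor does the troponin rule only remove positives: Step 4 shows that it works in both directions, and it applies only when several assays exist at one visit.

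None of this explains why the protocol's summaries were dropped without being listed in SAP 7.7.

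**Conclusion.** The point holds as an undeclared omission of descriptive safety summaries. ECG observed values, ECG change from baseline, ECG thresholds and vital-sign thresholds are in protocol 8.7.3 but absent from the SAP, and SAP 7.7 lists none of them. PR or QTc lengthening within normal limits, or progression of an abnormality already present at baseline, may therefore appear in no planned ECG summary. The documents do not support the wider claim that worsening in subjects with an abnormal baseline generally goes unseen.

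The likely impact is modest, for the reasons of prior evidence and ECG timing given above. The matter is still worth correcting because the correction is cheap and the protocol made the commitment.

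The conclusion rests on two unknowns. The documents do not say whether numeric intervals are in the database. The SAP is based on protocol amendment 2, and the version of the supplied protocol cannot be confirmed because its title page was removed.

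**What to change.** **SAP 7.5.** Add by-arm summaries of PR, QRS and QTcF, observed and change from baseline, with Days 2 to 14 kept apart from Day 28. State the number of subjects with an ECG in each period. Add counts by the Appendix 5 PR and QTc grades, including the QTc increase criteria. Define what counts as a new abnormality, and say how worsening of an existing one is classified.

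**SAP 7.3.** Add vital-sign threshold counts, using the Appendix 5 grades where they exist (for example hypertension and fever). Where the appendix gives no numeric grade, as for pulse and respiratory rate, state the cut-offs before unblinding.

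**If intervals are not in the database.** Enter them from the ECG tracings and reports already collected under protocol 6.7.8, or declare and justify the omission in SAP 7.7.

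**SAP 7.6 (minor).** Where several troponin assays exist at a visit, use the same assay as at baseline instead of always Troponin I.

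**Cost.** A few extra tables and a sentence on troponin. If data entry is needed, about 60 subjects with 2 to 3 protocol ECGs each gives 60 × 2 = 120 to 60 × 3 = 180 ECGs, plus any done as standard of care. Declaring the omission alone would take a paragraph in SAP 7.7.

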### **7.6. Other Safety Measures**

A shift table of troponin results at postbaseline visit (including those obtained for the purposes of standard medical care) compared with baseline values will be presented by treatment group using the following categories: normal, abnormal, or missing. The number and percentage of subjects in each cross-classification group of the shift table will be presented. Subjects with a missing value at baseline or postbaseline will not be included in the denominator for percentage calculation. No formal statistical testing is planned.

If multiple troponin results exist for one visit due to multiple troponin assay tests performed, the results obtained from Troponin I test will be used for the analysis.

A by-subject listing for all troponin results, including those not required by the protocol (ie, standard of care), will be provided by subject ID number and visit in chronological order.

A data listing will be provided for subjects experiencing pregnancy during the study.

#### **7.7. Changes From Protocol-Specified Safety Analyses**

In accordance with the DMC Charter, the initial safety DMC meeting was scheduled to occur after approximately 50% of the subjects were enrolled. The winter 2016/2017 RSV season resulted in a higher rate of enrollment for this study compared to previous RSV seasons. Due to quicker than expected enrollment and the time required to prepare for a DMC meeting, it would not have been possible to hold the planned DMC meeting prior to all subjects completing treatment with presatovir. Since the findings of the DMC would not have been actionable upon subjects in the study, the DMC Chairperson agreed to forgo the meeting

## 8. PHARMACOKINETIC (PK) ANALYSES

Individual subject concentration data for presatovir will be listed and summarized using descriptive statistics. Summary statistics (n, mean, SD, coefficient of variation [%CV], median, min, max, Q1, and Q3) will be presented for individual subject concentration data by time point.

Individual concentration data listings and summaries will include all subjects with concentration data. The sample size for each time point will be based on the number of subjects with nonmissing concentration data at that time point. The number of subjects with concentration BLQ will be presented for each time point. For summary statistics, BLQ values will be treated as 0 at predose and one-half of the lower LOQ for postdose time points.

The following table will be provided for presatovir:

- Individual subject concentration data and summary statistics

The following figures will be provided for presatovir:

- Mean ( $\pm$  SD) concentration data versus time (on linear and semilogarithmic scales)

Individual, mean, and median postdose concentration values that are  $\leq$  lower LOQ will not be displayed in the figures and remaining points connected.

PK sampling details by subject, including procedures, differences in scheduled and actual draw times, and sample age will be provided in listings.

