- Blood specimens for safety labs include measures of the subject's sodium, potassium, chloride, CO₂, BUN, creatinine, glucose, AST, ALT, alkaline phosphatase, total bilirubin, creatine kinase (CK), and complete blood count (CBC). These are measured on Days 1/Baseline, 7, 14, 21, and Day 28/End of Study and will be collected from all subjects. Additionally, blood specimens for local troponin testing will be collected from all subjects at Day 1/Baseline, Day 28/ End of Study, and if the subject is seen at the site for any reason (eg, hospitalization, clinic, or site visit) between Days 2 to 14. Refer to Section 6.7.6 for additional information.
- Blood specimens for HLA (human leukocyte antigen) antibodies will be collected from all subjects on Day 1/Baseline and Day 28/End of Study.
- Blood specimens for RSV antibody titers will be collected from all subjects on Day 1/Baseline and Day 28/End of Study.

- Blood specimens for PK measurements will be collected from all subjects at the following time points: 2-4 hours post-dose at Day 1/Baseline, pre-dose on Days 7 and 14, and any time on Day 21. A PK sample will be collected if a subject early terminates from the study prior to Day 21.
- Blood specimens for plasma biomarker measurements (Type 1 CXCL9, 10, 11, IL-18, IL-12, p70, TNF- α , Type 17 - CCL2 [MCP-1], CCL3 [MIP1 α], CCL5 [RANTES], CCL11 [Eotaxin], TGF- β , IL-17, CCL20, IL-1 β , IL-1ra, IL-6, IL-12 p40 and IL-23) will be collected from all subjects on Days 1/Baseline, 7, 14, and 21.

- PPD

Spirometry: Spirometry testing measurements, obtained by certified respiratory therapists or other nurses/technicians trained in pulmonary function testing, will be obtained at Screening or on Day 1/Baseline and Day 28/End of Study.

The study Day 1/Baseline forced expiratory volume in 1 second (FEV₁) and forced vital capacity (FVC) must be obtained *prior to IMP administration*. Alternatively, measures of FEV₁ and FVC obtained for the purposes of patient care within 2 days prior to Day 1/Baseline may be used to satisfy the Screening / Day 1/Baseline spirometry measurements. However, these tests must have been obtained at the same site of subject enrollment and the same spirometry machine should be utilized for the Day 28/End of Study measurement.

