1.4. Dose Rationale

The dose and administration schedule selected for this study is a single dose of 200 mg presatovir administered orally or via NG tube on Day 1/Baseline, followed by 100 mg once daily on Days 2 through 14. This regimen was selected based upon the PK characteristics of presatovir and the pharmacokinetic/pharmacodynamic (PK/PD) relationship established in the antiviral effect study with different doses/regimens in Study GS-US-218-0103.

In Study GS-US-218-0103, a 5-day treatment regimen of presatovir (50 mg single dose on Dose Day 1, followed by 25 mg once daily on Dose Days 2 through 5) resulted in a significant reduction in RSV viral load. The mean AUC of RSV viral load as measured by the RT-qPCR assay from first viral load measurement post initial dose of study drug through end of quarantine (Day 12) was significantly lower in presatovir subjects compared to placebo subjects ($\Delta = 506.9 \log_{10} \text{PFUe} \cdot \text{hour/mL}$, $p < 0.001$). This 5-day regimen achieved presatovir trough concentrations ~4-5 fold higher than the paEC_{95} (52 ng/mL) for up to 120 hours following dose initiation for RSV M37 (virus strain used in GS-US-218-0103 study).

The dose for the current study was selected with the goal to maintain the plasma trough concentration of presatovir at least 5-fold above the paEC_{95} (25 ng/mL) of the clinical RSV isolates for the duration of RSV shedding in LT patients. Longitudinal viral dynamics data in LT patients with RSV is limited and is reported as a part of randomized trials and epidemiologic studies. Two trials indicate the majority of patients shed RSV for an average of 5.5 days {[Zamora et al 2011](#)} {[Simon et al 2012b](#)} {[Simon et al 2012a](#)}; however, the time of enrollment from onset of symptoms was variable and in some cases substantial. Moreover, immunosuppressed patients with RSV infection are demonstrated to shed virus for 21 days or longer {[Chemaly et al 2014](#)} {[Lehners et al 2013](#)} {[Geis et al 2013](#)}. The dose and schedule in the current study, 200 mg on Day 1/Baseline followed by 100 mg daily on Days 2 through 14, will maintain plasma levels of presatovir greater than 5-fold above paEC_{95} for at least 18 days after the first dose.

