6.5.1. Assessments for Premature Discontinuation from IMP Administration

If a subject prematurely discontinues IMP dosing, the subject will remain on study and will continue with all subsequent study visits and assessments through Day 28/End of Study Visit, with the exception of IMP administration.

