8.8. Pharmacokinetic Analysis

Concentrations of presatovir will be determined in plasma using a validated Bioanalytical assay. Individual subject presatovir concentration-time data will be displayed using scheduled sampling times. Descriptive statistics (eg, n, mean, standard deviation, %CV, median, and range) will be calculated for each sampling time. The pharmacokinetic/pharmacodynamic (PK/PD) relationship may be explored as appropriate.

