### **3.7. Data Handling Conventions and Transformations**

In general, age (in years) on the date of the first dose of study drug will be used for analyses and presentation in listings. If an enrolled subject was not dosed with any study drug, the randomization date will be used instead of the first dosing date of study drug. For screen failures, the date the informed consent was signed will be used for age calculation. If only the birth year is collected on the eCRF, “01 January” will be used for the unknown birth day and month for the purpose of age calculation. If only birth year and month are collected, “01” will be used for the unknown birth day.

Non-PK data that are continuous in nature but are less than the lower limit of quantitation (LOQ) or above the upper LOQ will be imputed as follows:

- A value that is 1 unit less than the LOQ will be used to calculate descriptive statistics if the datum is reported in the form of “< x” (where x is considered the LOQ). For example, if the values are reported as < 50 and < 5.0, values of 49 and 4.9, respectively, will be used to calculate summary statistics. An exception to this rule is any value reported as < 1 or < 0.1, etc. For values reported as < 1 or < 0.1, a value of 0.9 or 0.09, respectively, will be used to calculate summary statistics.
- A value that is 1 unit above the LOQ will be used to calculate descriptive statistics if the datum is reported in the form of “> x” (where x is considered the LOQ). Values with decimal points will follow the same logic as above.
- The LOQ will be used to calculate descriptive statistics if the datum is reported in the form of “≤ x” or “≥ x” (where x is considered the LOQ).

If methods based on the assumption that the data are normally distributed are not adequate, analyses may be performed on transformed data or nonparametric analysis methods may be used, as appropriate.

Plasma concentration values that are below the limit of quantitation (BLQ) will be presented as “BLQ” in the concentration data listing. Values that are BLQ will be treated as 0 at pre-dose time points, and one-half the value of the LOQ at post-baseline time points.

The following conventions will be used for the presentation of summary and order statistics:

- If at least 1 subject has a concentration value of BLQ for the time point, the minimum value will be displayed as “BLQ.”

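### Day 7 and Day 14 pre-dose concentration summaries will mix on-drug samples with samples from subjects who have stopped study drug

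*SAP*

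**What the plan says.** The protocol synopsis and Table 6-1 schedule plasma samples at "2-4 hours post-dose at Day 1/Baseline, pre-dose on Days 7 and 14, and any time on Day 21". Nothing is drawn before the first dose, so Days 7 and 14 are the only scheduled pre-dose points.

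Under Protocol 6.5.1, when study drug is stopped early, "the subject will remain on study and will continue with all subsequent study visits and assessments through Day 28/End of Study Visit", without further dosing. The Day 7 and Day 14 PK draws are among those assessments.

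SAP 8 then states: "Individual concentration data listings and summaries will include all subjects with concentration data". It adds: "The sample size for each time point will be based on the number of subjects with nonmissing concentration data at that time point". Protocol 8.8 says: "Individual subject presatovir concentration-time data will be displayed using scheduled sampling times". The PK Analysis Set (SAP 3.1.5) asks for evaluable on-study measurements in subjects with at least one full dose. It does not define evaluable and does not require the subject to be on treatment. Protocol 8.3 limits the summary statistics by subject, not by sample. SAP 3.8.2 assigns early-termination data to the next scheduled visit at which those data were due.

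On values below the limit of quantification, SAP 3.7 says: "Values that are BLQ will be treated as 0 at pre-dose time points, and one-half the value of the LOQ at post-baseline time points". SAP 8 draws the line between predose and postdose instead.

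Protocol 1.4 sets the exposure goal: "The dose for the current study was selected with the goal to maintain the plasma trough concentration of presatovir at least 5-fold above" a paEC95 of 25 ng/mL.

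**The concern.** A Day 14 pre-dose concentration will normally be read as an on-treatment trough. For a subject who stopped a week earlier it is a washout value, yet the planned summary treats the two alike. The early-termination rule adds a second route: a sample taken at withdrawal between Day 7 and Day 14, with no required relation to a dose, can be carried to Day 14.

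The protocol expects some subjects to stop. Section 3.5 lists the events that prompt review of dosing, and Section 5.1.1 ends study treatment when the assignment is disclosed to the investigator.

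Pharmacokinetics is a secondary objective, and Days 7 and 14 are the direct check of the exposure goal in lung transplant recipients. Mixed samples would lower the minimum, inflate the %CV and show individuals below the goal who were simply off drug. They would also carry the wrong exposure into any PK/PD exploration.

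**Working it through.** **Inputs from the documents.** Half-life about 36 h on multiple dosing, 30 to 33 h after single doses (Protocol 1.2.4.1). Exposure approximately proportional to dose (same section). Trough on the 50/25 mg regimen 4 to 5 times 52 ng/mL, that is 208 to 260 ng/mL (Protocol 1.4). Goal 5 × 25 = 125 ng/mL. Presatovir subjects 60 × 2/3 = 40.

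**Assumptions.** One-compartment decay; 1, 4 or 6 of 40 off drug; on-drug CV 30%; assay limit 0.1 to 10 ng/mL. The documents give none of these.

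**Model.** Each dose contributes dose × 2^(−hours since dose / half-life), with a first dose of 2 units and later doses of 1 unit.

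**Step 1: reproduce the plan's figure.** Protocol 1.4 says levels stay more than 5-fold above paEC95 for at least 18 days. At 36 h the relative trough is 1.633 at 120 h (5 doses) and 1.701 at 312 h (13 doses, Day 14 pre-dose). Scaling 25 mg to 100 mg multiplies 208–260 by 4, giving 832–1040 ng/mL at 120 h. The Day 14 trough is then 832 × 1.701/1.633 = 867 to 1040 × 1.701/1.633 = 1083 ng/mL. The level one day after the Day 14 dose is about the same, and the time from there to 125 ng/mL is 36 × log2(867/125) = 101 h to 36 × log2(1083/125) = 112 h. That gives 18.2 to 18.7 days after the first dose, so the figure reproduces. At 30 h it is 17.4 to 17.8 days, slightly short.

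**Step 2: one subject off drug.** Last dose on Day 7, sampled on Day 14: the relative level is 0.105, and 0.105/1.701 = 6.2% of the on-drug trough. Simple decay gives nearly the same: 2^(−144/36) = 6.25%. In concentration, 0.062 × 867 = 54 to 0.062 × 1083 = 67 ng/mL, below 125. At 30 h the share is 3.6%.

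Timing matters. Stopping after dose 10 leaves about 25% on Day 14 (216 to 270 ng/mL, above the goal). On Day 7, stopping after dose 1, 3 or 5 leaves 7.5%, 23% or 62%.

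**Step 3: group mean.** With fraction p off drug at share r = 0.062, the mean ratio is 1 − p(1 − r), and CV² = (1 + 0.30²)(1 − p + p r²)/mean² − 1.

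| Off drug since dose 7 | Day 14 mean vs on-drug | CV (from 30%) |
|---|---|---|
| 0 of 40 | 100% | 30% |
| 1 of 40 | 1 − 0.025 × 0.938 = 97.7% | 34% |
| 4 of 40 | 1 − 0.10 × 0.938 = 90.6% | 44% |
| 6 of 40 | 1 − 0.15 × 0.938 = 85.9% | 51% |

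On Day 7, off drug since dose 3, the corresponding means are 98.1%, 92.3% and 88.5%.

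**Step 4: against the goal.** With 4 of 40 the Day 14 mean is 0.906 × 867 = 785 to 0.906 × 1083 = 981 ng/mL, still 6.3 to 7.8 times 125.

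**Step 5: median.** With the lowest 10% displaced, the overall median is the (0.50 − 0.10)/0.90 = 44th percentile of on-drug values. For a lognormal with CV 30% (log-scale SD 0.294), that is exp(−0.294 × 0.140) = 0.96, a fall of about 4%.

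**Step 6: BLQ rule.** From a mid-range trough of about 975 ng/mL, reaching 10 ng/mL takes about 11 days from the last dose, and reaching 1 ng/mL about 16 days. If 4 of 40 were BLQ at a limit of 10 ng/mL, replacing 0 by LOQ/2 would add 4/40 × 5 = 0.5 ng/mL, or 0.5/975 = 0.05% of the mean.

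**The case against.** The strongest reply is that little hangs on these summaries. No PK hypothesis is tested, the SAP names no trough parameter and plans no target-attainment analysis, and PK/PD work is optional. The plan reports the median and tabulates individual concentrations. Listings of drug administration, premature discontinuation and PK sampling let a reader trace a low value. The terms *evaluable* and protocol-specified sampling time (Table 15.10.1.1) might also be used to drop a sample with no dose to follow.

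Most of this limits the importance of the point without removing it. The undefined terms may be applied either way, and the explicit sentence in SAP 8 favours inclusion. The PK listing shows deviation from the scheduled draw time, not time since last dose, so a punctual sample a week after stopping looks normal until it is matched with another listing.

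The objection to the size also stands: the stopping rate is assumed, and 30% is what Protocol 1.2.4.1 gives for most PK parameters in healthy volunteers, not a trough CV. With an assumed on-drug CV of 60%, 4 of 40 would raise it only to about 70%.

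Three stronger readings are tempting and are not supported:

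- A reader might infer that the lowered mean would put the dose rationale in doubt. Step 4 shows that it would not.
- A reader might infer that setting BLQ to zero biases the trough. BLQ should be rare at these visits and the shift is at most about 0.05%. Moreover, SAP 3.7 can be read as giving LOQ/2 there, since Days 7 and 14 are both pre-dose and post-baseline. That is a wording conflict only.
- A reader might want a fixed window such as 20 to 28 h after the previous dose. The documents contain no such window. Days 6 and 13 have no required visit, and nothing shows that clock times of home doses are recorded. A 30 h sample would be only 1 − 2^(−6/36) = 11% below a 24 h one, so the window could discard valid on-drug samples.

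**Conclusion.** The point holds as a gap in the PK summary rule. As written, the plan places off-drug samples, and possibly reassigned early-termination samples, in the only pre-dose summaries, and no stated rule clearly removes them. The fall in the mean is somewhat less than the share of subjects off drug, approaching it when they stopped well before the visit. The minimum, the %CV and individual comparisons with 125 ng/mL are the most exposed; the median moves less than half as much as the mean in the 4-of-40 case. The size rests on the assumed number and timing of stops, the assumed on-drug CV and one-compartment decay. No efficacy or safety conclusion is affected. The BLQ inconsistency is real but numerically negligible.

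**What to change.** In SAP 8, define *evaluable* at sample level. The Day 7 and Day 14 pre-dose summaries and the mean concentration figure should exclude (a) samples drawn after permanent discontinuation of study drug and (b) early-termination samples not drawn pre-dose on treatment. Judge both from recorded dosing dates, not from a fixed hour window. Subjects still on treatment who missed a dose stay in, because removing them would bias the summary upward. List excluded samples with time or days since last dose, and keep an all-samples summary as supportive.

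Separately, use one BLQ rule in SAP 3.7 and SAP 8: LOQ/2 for every sample after the first dose, and 0 only before the first dose.

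The cost is SAP wording, a programming filter and one supportive table, with a slightly smaller n at each pre-dose point. Trial conduct and data collection do not change.
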